Statistical Analysis Plan (Addendum)

Increasing Knowledge of Alcohol as a Risk Factor for Breast Cancer Among Women Attending Breast Screening Services (Health4Her)

ClinicalTrials.gov Identifier: NCT04715516.

Pre-registered: Wednesday 20 January 2021

Version: 1

Date version finalised: Friday 18 February 2022

Study rationale and design

Alcohol is a major modifiable risk factor for breast cancer in women, yet this is not widely understood by health practitioners or policy makers, let alone the general population. We planned to undertake a pragmatic, single-site, double-blind, parallel group randomised controlled trial to test the effects of an alcohol brief intervention among women attending breast screening services, to improve knowledge of alcohol as a risk factor for breast cancer and reduce harmful alcohol use.

Women attending Maroondah BreastScreen for routine mammography (N = 558) completed a baseline assessment before being randomised to receive 4 minutes of alcohol brief intervention plus 3 minutes of lifestyle health promotion (active arm, n = 279), or 3 minutes of lifestyle health promotion, not inclusive of alcohol information (control arm, n = 279). For the active arm, participant responses to questions about current alcohol use branched to personalised feedback consistent with level of alcohol consumption (i.e. drinking within or above current Australian Alcohol Guidelines). Interventions were delivered by way of an animation on an iPad. Both groups also received take-home information pertaining to group assignment. Follow-up assessments were completed by telephone at 4- and 12-weeks post-randomisation.

Statistical Analysis Plan (SAP)

This plan, or SAP Addendum, provides additional detail to the statistical considerations that were documented in the statistical analysis plan in Health4Her Protocol_V7_08 08 21 (available in the trial record on ClinicalTrials.gov).

Data will be collated, cleaned and validated using programmed edit checks.

Outcomes with measurements at more than two time points

In general, outcome variables with repeated measurements will be analysed by fitting linear mixed models (for continuous outcomes or outcomes treated as continuous, such as 5-point Likert scales) or (for categorical / binary outcomes) generalised linear mixed models (GLMMs) or generalised additive mixed models (GAMMs), with fixed effects for treatment and time, and their interaction, and random effects for subjects and assessments within subjects, using restricted maximum likelihood (REML) or similar algorithms. These models allow missing values to be accommodated.

These methods will allow the most suitable variance-covariance model for the repeated measures to be selected, using Akaike's Information Criterion, and, if appropriate, commonality of nonlinear trends over time to be explored via splines. The F-test (or equivalent chi square test, t-test of coefficients in logistic regression) will be used to test for an overall group by time interaction in outcomes measured at all three follow-up times (0, 4 and 12 weeks).

Outcomes measured at two or fewer time points

For outcome variables measured at two or fewer time-points, different models will be used, depending on the nature of the outcome variable:

- Where the outcome is binary and proportions are required, a test of change in proportions for categorical outcomes, e.g. the Cochran-Mantel-Haenszel test, will be applied or, if covariates are required in the analysis, logistic regression with random effects for subjects. Such logistic regression models are instances of GLMMs or GAMMs.
- 2. For continuous outcomes or outcomes treated as continuous (such as 5-point Likert scales) linear mixed models will be used (as for outcomes measured at three time-points).
- 3. In simple cases of the preceding points, the analysis may reduce to (in the sense of being equivalent to) a test of whether there is a difference between the two groups (treatment and control) in the changes in the mean (for continuous outcomes). If just one time point is involved, we may use a binomial test of proportions (for categorical outcomes).

Outcomes measured at 4 and 12 weeks but without a baseline measurement will be covered by this case.

Missing values

Where possible, missing values will be handled under the missing at random assumption; that is, unless there is good reason to believe this assumption is untenable. In cases of doubt the analysis will be re-done with (a) missing values imputed and (b) the corresponding subjects removed from the analysis.

Outcomes where there is no baseline measure possible (that is, by design) will not be treated as having the baseline value missing, but rather as belonging to the two time-point case.

Exploratory analyses

Exploratory analyses will be performed using the same methods as for the primary and secondary outcomes (as appropriate) plus, optionally, such other modelling strategies as may be useful (e.g. random forests or decision trees as exploratory tools, or other classification tools).

In exploratory analyses of outcomes measured at three time-points, mixed models with covariates as relevant (see list of potential covariates below), including their interactions with treatment group, will be fitted in order to identify moderating factors. Categorical, ordinal and binary outcomes will be analysed in a similar way using generalised linear mixed models (GLMMs) or generalised additive mixed models (GAMMs).

In exploratory analyses of outcomes measured at two time-points, logistic regression with random effects for subjects will be utilised to assess the effects of potential covariates (see list of potential covariates below).

Statistical software

Analyses will be conducted using the most appropriate procedures in GenStat, R, SAS or STATA and additional analyses not specified in the published protocol or this addendum will be regarded as exploratory.

Statistical Analysis of the Primary and Key Secondary Outcome Variables

Primary Outcome

The primary analysis will take place after all subjects, not known to have withdrawn or not deemed lost to follow-up, have had their 12-week assessments, based on the intention to treat (ITT) principle (i.e. subjects' data are analysed as randomised and as stratified).

The primary outcome of this repeated measures RCT is the proportion of participants accurately identifying alcohol as a clear risk factor for breast cancer at 4-weeks post-randomisation. Inferences about the effect of the Health4Her intervention on the primary outcome will be based on a comparison, between treatment groups, of change from baseline to 4-weeks post-randomisation using a Cochran-Mantel-Haenszel test. This analysis tests for homogeneity of the odds ratio across strata (i.e. intervention and control). A binomial test (that is, a test of proportions) will be used as an ancillary analysis of the primary outcome (i.e. the difference in proportions between the two groups at 4-weeks post-randomisation).

Relevant covariates (from the list of potential covariates below) may also be used in further analysis, using generalised linear models (logistic regression) to make comparisons. Additional analyses may use covariates for post-stratification.

Secondary Outcomes

Alcohol Consumption

Alcohol consumption will be assessed by the Alcohol 14-day Timeline Follow-back (TLFB). Heavy drinking days are measured as >40 grams of alcohol (>4 Australian standard drinks). Alcohol consumption will also assessed by the AIHW alcohol frequency quantity items. Assessments are made at 0, 4 and 12 weeks and linear mixed models (continuous variables) or GLMMs or GAMMs (categorical / binary variables) will be used. The following outcomes will be analysed (transformed if necessary for analysis):

Secondary outcome 1 – Proportion of participants drinking less than or equal to 10 standard drinks per week at 4-weeks and 12-weeks post-randomisation. Derived from (operationalised in two ways):

- Has the participant consumed >10 standard drinks in week one AND/OR >10 standard drinks in week two? (tlfb_nhmrc_both_comprh)
- Has the participant consumed >10 standard drinks in both week one AND week two? (derived variable: tlfb_nhmrc_bothwks)

Secondary outcome 2 – Proportion of participants drinking less than or equal to 10 standard drinks per week at 4-weeks and 12-weeks post-randomisation, among only participants who drink more than 10 standard drinks per week at baseline.

Subgroup defined as either i. women who consumed >10 standard drinks in week one AND/OR >10 standard drinks in week two (tlfb_nhmrc_both_comprh) or ii. women who consumed >10 standard drinks in both week one AND week two (tlfb_nhmrc_bothwks).

Outcome derived from:

- Has the participant consumed >10 standard drinks in week one AND/OR >10 standard drinks in week two? (tlfb_nhmrc_both_comprh)
- Has the participant consumed >10 standard drinks in both week one AND week two? (tlfb_nhmrc_bothwks)

Secondary outcome 3 – Change in alcohol consumption at 4-weeks and 12-weeks post-randomisation. Derived from:

- TLFB: Drinking Days (tlfb_drinkdays)
- TLFB: Drinking Days with > 2 Standard Drinks (tlfb_days_2stand)
- TLFB: Drinking Days with > 4 Standard Drinks (tlfb_days_4stand)
- TLFB: Total Standard Drinks in the Past 14 days (tlfb_totalmonth)
- Derived from AIHW frequency quantity items: average standard drinks per day (derived variable: alc_perday)
- AIHW frequency: In the past month, how often did you have an alcoholic drink of any kind? (alc_freq)
- AIHW quantity: quantity of alcohol consumed on a typical day calculated in standard drinks (alc_quant_sd)

Secondary outcome 4 – Change in alcohol consumption at 4-weeks and 12-weeks postrandomisation, among only participants who drink more than 10 standard drinks per week at baseline

Subgroup defined as either i. women who consumed >10 standard drinks in week one AND/OR >10 standard drinks in week two (tlfb_nhmrc_both_comprh) or ii. women who consumed >10 standard drinks in both week one AND week two (tlfb_nhmrc_bothwks).

Outcome derived from:

- TLFB: Drinking Days (tlfb_drinkdays)
- TLFB: Drinking Days with > 2 Standard Drinks (tlfb_days_2stand)
- TLFB: Drinking Days with > 4 Standard Drinks (tlfb_days_4stand)
- TLFB: Total Standard Drinks in the Past 14 days (tlfb_totalmonth)
- Derived from AIHW frequency quantity items: average standard drinks per day (alc_perday)
- AIHW frequency: In the past month, how often did you have an alcoholic drink of any kind? (alc_freq)
- AIHW quantity: quantity of alcohol consumed on a typical day calculated in standard drinks (alc_quant_sd)

Alcohol health literacy

Secondary outcome 5 – Change in participants' attitudes regarding alcohol and breast cancer risk from baseline to 4-weeks post-randomisation. A linear mixed model (for repeated measures) will be used to analyse the Likert scale response (derived from atttd_alcrisk). Transformations of response variables will be used as appropriate, such as in GLMMs or GAMMs.

Secondary outcome 6 – Proportion of participants accurately identifying i) the amount of alcohol in an Australian standard drink; ii) the number of standard drinks in an average restaurant serve of red wine; iii) the maximum number of standard drinks per week recommended by current Australian alcohol guidelines, at 4-weeks post-randomisation).

Analyses will be the comparison, between treatment groups, of change from baseline to 4-weeks post-randomisation using a Cochran-Mantel-Haenszel test. Relevant covariates (from the list of potential covariates below) may also be used in further analysis, using generalised linear models (logistic regression) to make comparisons. Additional analyses may use covariates for post-stratification. A binomial test (that is, a test of proportions) may be used as an ancillary analysis of the outcome (i.e. the difference in proportions between the two groups at 4-weeks post-randomisation), with logistic regression as an option if covariates are employed.

Outcome derived from:

- Proportion of participants who accurately respond to "In Australia, a standard drink contains
 ____ grams of alcohol" knowl_sd = 1 (10 grams)
 - recode to binary variable (1 = accurate | 2 = not accurate)
- Proportion of participants who accurately respond to "An average restaurant serve of red wine contains..." knowl_redwine = 3 (1.6 standard drinks)
 - recode to binary variable (1 = accurate | 2 = not accurate)
- Proportion of participants who accurately respond to "According to the latest Australian alcohol guidelines, it is recommended that healthy women should drink no more than _______standard drinks per week." knowl_alcguideline = free-text response of "10"
 - recode to binary variable (1 = accurate | 2 = not accurate)

Secondary outcome 7 – Proportion of participants who have accessed health information on i) alcohol harms, ii) alcohol and breast cancer risk, and iii) alcohol harm-reduction.

A binomial test (that is, a test of proportions) will be used (i.e. the difference in proportions between the two groups at 12-weeks post-randomisation), with logistic regression as an option if covariates are employed.

Outcome derived from info_sought_catg = 1 (alcohol) and/or 2 (alcohol and breast cancer risk) and/or 3 (alcohol and other health risks) and/or 4 (alcohol and women's health)

- recode to binary variable (1 = accessed | 2 = did not access)

(NB. This outcome is described in the ClinicalTrials.gov trial registration as assessed at 4-weeks post-randomisation, however to maintain blinding of Research Assistant these data were collected at 12-weeks post-randomisation.)

Quality of Life / health-related quality of life

Secondary outcome 8 - Change in general health/health-related quality of life at 4- and 12-weeks post-randomisation will be assessed using the SF-12.

Physical and mental component summary scores will be derived from SF-12 variables (sf12_health, sf12_activmod, sf12_activstair, sf12_physless, sf12_physlimit, sf12_emoless, sf12_emocaref, sf12_pain, sf12_calm, sf12_energy, sf12_down, sf12_interf).

Weighting coefficients for computing the scores will be those specified in Tucker et al (2010)ⁱ.

Linear mixed models (for repeated measures) will be used to analyse the continuous responses (derived from the two SF-12 scores). Transformations of response variables will be used as appropriate.

Secondary outcome 9 – Change in quality of life at 4- and 12-weeks post-randomisation will be assessed using the EUROHIS-QOL single item. Linear mixed models (for repeated measures) will be used to analyse the Likert scale response (derived from eurohis_qol1). Transformations of response variables will be used as appropriate.

Potential additional exploratory analyses

As above, for repeated measures outcomes, linear mixed models or GLMMs or GAMMs will be used (or test of change in proportions for categorical outcomes, e.g. Cochran-Mantel-Haenszel test). When examining differences between groups at one follow-up time point (i.e. non-repeated measures), a binomial test will be used to test the difference in proportions between the two groups.

- i. Change in the proportion of women who identify alcohol as a risk factor for breast cancer without prompt (0 and 4-weeks post-randomisation)
 - derived from knowl_alc
 - binary variable, Y | N
- ii. Change in the proportion of women who identify inactivity as a risk factor for breast cancer without prompt (0 and 4-weeks post-randomisation)
 - derived from knowl_inactiv
 - binary variable, Y | N

- iii. Change in the proportion of women who identify excess weight as a risk factor for breast cancer without prompt (0 and 4-weeks post-randomisation)
 - derived from knowl_weight
 - binary variable, Y | N
- iv. Change in total minutes of physical activity in the past week (0, 4-week and 12-week post-randomisation)
 - derived from phys_activetotal
 - continuous variable
- v. Proportion of women reporting a perceived change in physical activity (4-week and 12-week variable only, no baseline)
 - derived from phys_change
 - categorical variable, 1 = more physically active | 2 = less physically active | 3 = about the same
- vi. Proportion of women reporting a perceived improvement in physical activity (4-week and 12-week variable only, no baseline)
 - derived from phys_change
 - recode categorical variable, 1 = more physically active | 0 = not more physically active
- vii. Change in past-week vegetable intake (0, 4-week and 12-week post-randomisation)
 - derived from veg_intake
 - continuous variable, days out of 7 days
- viii. Change in past-week fruit intake (0, 4-week and 12-week post-randomisation)
 - derived from fruit_intake
 - continuous variable, days out of 7 days
- ix. Proportion of participants accurately identifying inactivity as a clear risk factor for breast cancer (0 and 4-weeks post-randomisation)
 - derived from bcriskfact_inactive
 - recode to binary variable (1 = identified as a clear risk factor | 2 = not identified as a clear risk factor)
- x. Proportion of participants accurately identifying alcohol as a clear risk factor for breast cancer (0 and 4-weeks post-randomisation)
 - derived from bcriskfact_alc
 - 4-level categorical variable (1 = clear risk factor | 2 = possible risk factor | 3 = not a proven risk factor | 4 = unsure)
- xi. Proportion of participants accurately identifying overweight as a clear risk factor for breast cancer (0 and 4-weeks post-randomisation)
 - derived from bcriskfact_ovweight

- recode to binary variable (1 = identified as a clear risk factor | 2 = not identified as a clear risk factor)
- xii. Change in knowledge of exercise as a bc risk factor (0 and 4-weeks post-randomisation)
 - derived from knowl_exercise
 - accurate response knowl_exercise = 2 (at least 2.5 hours)
 - recode to binary variable (1 = accurate | 2 = not accurate)
- xiii. Change in knowledge of diet as a bc risk factor (0 and 4-weeks post-randomisation)
 - derived from knowl_diet
 - accurate response knowl_diet = 1 (dairy)
 - recode to binary variable (1 = accurate | 2 = not accurate)
- xiv. Change in attitude "It is important that I understand the risk factors for breast cancer" (0 and 4-weeks post-randomisation)
 - derived from atttd_riskundrstnd
 - Likert response
- xv. Change in attitude "I believe I am able to change my risk of breast cancer" (0 and 4-weeks post-randomisation)
 - derived from atttd_changerisk
 - Likert response

Potential covariates for exploratory analyses of primary and secondary outcomes

- age (continuous; categorical 40-49, 50-59, 60-69, 70+ years)
- lgbtq+
- education
- born in Australia
- culturally and linguistically diverse background
- household composition
- disability status
- alcohol consumption at baseline (drinking above/within current NHMRC guidelines, 14-day TLFB subscales scores, AIHW frequency quantity scores)
- QoL/health-related QoL at baseline (SF-12 mental and physical component scores, EUROHIS-QOL single item)
- health literacy at baseline (attitude and knowledge scores)

ⁱGraeme Tucker, Robert Adams, David Wilson. New Australian population scoring coefficients for the old version of the SF-36 and SF-12 health status questionnaires, Qual Life Res (2010) 19:1069-1076, DO 10.1007/s11136-010-9658-9

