## 2 INTRODUCTION AND BACKGROUND

Alcohol use is a major modifiable risk factor for breast cancer in women, even in low amounts, with evidence of a clear dose-response relationship. Indeed, meta-analyses reveal that the relative risk of breast cancer increases by 4%, 23% and 61% for light, moderate and heavy alcohol consumption, respectively (Bagnardi, 2015).

Women who are eligible for mammography are typically aged 50-74 years and, due to their age, are at increased risk for breast cancer (McPherson, 2000; White, 2014). This is a population who are particularly vulnerable to the harmful effects of alcohol. While breast cancer mortality has reduced by 28-30% due to earlier detection (Roder, 2008) and improved treatment protocols (Burton, 2012), a key health promotion and disease prevention strategy is to reduce women's drinking (WHO, 2017).

In Australia, awareness of the link between alcohol and breast cancer is surprisingly low (Bowden, 2014). While recommended upper limits of alcohol use are emerging as too generous, and associated with increased breast cancer risk, this is not widely understood even by health practitioners or policy makers, let alone the general population (Simapivapan, 2017). Low health

---

literacy regarding alcohol is a significant barrier to making informed decisions about reducing one's alcohol use (Rundle-Thiele, 2013).

Risky alcohol use – including daily drinking – is most common and stable among this cohort (AIHW, 2016; Daly, 2009), yet remains largely under-detected (O'Connell 2003). As such, a large proportion of women do not receive information, advice or effective intervention. Delivering a targeted health promotion strategy aimed at reducing alcohol consumption, within the context of an already institutionalised breast screening program, represents a unique opportunity to prevent alcohol-attributable harm in a large population for which there is great potential for health gain.

Internationally, computerised alcohol brief interventions (i.e. feedback on personal drinking levels compared with age/gender norms, alongside information about alcohol risks/harms) have received strong empirical support as a simple, cost-effective method of reducing drinking and related harm (Donoghue, 2014), and one which overcomes the logistical issues of providing intervention within busy healthcare environments.

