## 14 STATISTICAL METHODS

### 14.1 Sample Size Estimation

Since the aims of this pilot RCT include preliminary hypothesis testing for effectiveness, a power and sample size calculation has been performed (Moore, Carter et al. 2011). Power and sample size estimates were carried out using PS: Power and Sample Size Calculation V3.1.2 (Dupont and Plummer 1990), assuming a type 1 error probability of  $\alpha < 0.05$ , 2-tailed, and equal-sized groups. Power calculations are based on the primary endpoint, proportion of participants who accurately identify alcohol as a clear risk factor for breast cancer.

Our sample size estimation is based on our previous online survey study with 391 women who have attended/are eligible to attend breast screening services (Health4Her Phase I). If the proportion of control participants who accurately identify alcohol as a clear risk factor for breast cancer is 0.22 and the true response rate for participants receiving the alcohol brief intervention is 12% greater at 0.34, and compensating for 20% attrition at follow-up, then 548 participants (274 per arm) will provide power of 80% to be able to reject the null hypothesis.

Given the lack of definitive evidence regarding alcohol BI effects in women, and particularly women of middle- and older-age in a breast screening setting, this powered pilot RCT will inform the development of a subsequent, comprehensive multicentre trial. This pilot RCT will generate preliminary data on intervention response using exploratory surrogate/proximal markers of effectiveness (e.g. proportion of participants accurately identifying alcohol as a breast cancer risk factor, proportion of participants drinking within guidelines, alcohol consumption and well-being), and will provide concrete estimates of risky alcohol consumption prevalence, and expected rates of missing data and participant attrition specific to the population under study (Moore, Carter et al. 2011).

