### 14.2 Statistical Analysis Plan

A detailed statistical analysis plan will describe the statistical methods for each outcome as well as how missing data will be dealt with. Data will be collated, cleaned and validated, using programmed edit checks, in a database that will be locked prior to analyses. All statistical tests will be two-tailed, with alpha level set to 0.05. Statistical analyses will be adjusted for multiple comparisons when indicated. 95% confidence intervals will be reported throughout. All randomised participants will be included in the analysis (i.e. intention-to-treat) for primary and secondary outcomes. Demographic characteristics (e.g. age) and baseline measurements (e.g. knowledge of alcohol as a clear risk factor for breast cancer, alcohol consumption) will be summarised and reported by intervention arm. The analyses will examine change in outcomes over time (4-weeks and/or 12-weeks) relative to baseline. The complete details of the analyses will be specified in a Statistical Analysis Plan that will be reviewed and approved by a study team prior to database lock. Analyses will be conducted using the most appropriate procedures in R and STATA.

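### The mixed models for the continuous secondary outcomes leave the arm difference at baseline free, so they test differences in change; this is valid but gives away precision that baseline adjustment would recover

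*SAP*

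**What the plan says.** The SAP section on outcomes with more than two time points specifies linear mixed models "with fixed effects for treatment and time, and their interaction, and random effects for subjects and assessments within subjects". Week 0 is among the modelled times, and the F-test or its equivalent "will be used to test for an overall group by time interaction in outcomes measured at all three follow-up times". For continuous outcomes with two time points (secondary outcome 5, the attitude item), the next SAP section uses the same mixed model. It adds that in simple cases the analysis may reduce to "a test of whether there is a difference between the two groups (treatment and control) in the changes in the mean". Protocol section 14.2 likewise says that the analyses look at change relative to baseline.

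The SAP's design section states that women "completed a baseline assessment before being randomised", and protocol section 6 describes the same order.

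Neither document sets a common baseline mean, or names baseline as a covariate in the main analysis of these outcomes. Baseline alcohol use, quality of life and health literacy appear only in the SAP list headed "Potential covariates for exploratory analyses of primary and secondary outcomes".

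**The concern.** Because randomisation follows the baseline assessment, the two arms have the same true mean at week 0. A model with a treatment main effect and week 0 in the response ignores this. It estimates a baseline arm difference known to be zero and subtracts its sampling error from the follow-up comparison. The group-by-time terms are then change-score contrasts.

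Bias and type I error are not at issue, and neither is the choice of a joint test over both follow-up visits. What is at stake is power and interval width for the measures treated as continuous in secondary outcomes 3 and 4 (consumption), 5 (attitude), 8 (SF-12) and 9 (EUROHIS-QOL). The sample size was set on the binary primary outcome alone, so none of these has assured power.

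**Working it through.** **The plan's own figure.** The only design figure is 548 participants, for the primary outcome. With 0.22 against 0.34, two-sided 0.05 and 80% power, the uncorrected two-proportion formula gives 219 per arm; 219/0.8 = 273.75, so 274 per arm and 548 in total. It reproduces and is unaffected by this point. No figure is given for the continuous outcomes.

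**Inputs.** From the documents: 279 per arm (SAP design section), two-sided alpha 0.05 (protocol 14.2), and 20% attrition (protocol 14.1, "compensating for 20% attrition at follow-up"). Assumed: ρ = 0.3, 0.5, 0.7 and 0.8. The only hint is the protocol introduction, where risky drinking "is most common and stable among this cohort". That points loosely to the high end for drinking and says nothing about attitude or quality of life.

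**Is the planned contrast a change contrast?** Yes. A REML fit to complete simulated data (279 per arm, time as a factor) gave interaction coefficients of −0.158 and −0.129, equal to the raw differences in mean change. In 10,000 simulated null trials at each of ρ = 0.4, 0.6 and 0.8, type I error was 0.048 to 0.053 for change and 0.047 to 0.053 for the adjusted contrast.

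**Variance at one visit.** With baseline SD 1 and follow-up SD k, up to a common factor:

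- change: 1 + k² − 2ρk
- adjusted: k²(1 − ρ²)
- change minus adjusted: (1 − ρk)², never negative and zero only at ρ = 1/k

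At k = 1 the ratio adjusted/change is (1 − ρ²)/[2(1 − ρ)] = (1 + ρ)/2.

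**Single-visit power.** If the adjusted contrast has 80% power, its standardised effect is 1.960 + 0.842 = 2.802, and the planned power is Φ(2.802·√ratio − 1.960). At ρ = 0.3 this is Φ(2.802 × 0.806 − 1.960) = Φ(0.299) = 62%.

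**Joint 2-df test** (three-visit outcomes, compound symmetry, equal SDs, complete data). The ratio of noncentralities, planned/constrained, is (1 + 2ρ)/3 for an effect sustained at both visits and (2/3)(1 + 2ρ)/(1 + ρ) for an effect at week 4 only. Powers come from the noncentral chi-square on 2 df, with the constrained test set at 80%.

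**Missing data.** Generalised least squares with 279 per arm and 20% missing independently at each follow-up. The detectable week-4 difference is 2.802 × SE.

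| Assumed ρ | 0.3 | 0.5 | 0.7 | 0.8 |
|---|---|---|---|---|
| Variance ratio, k = 1, complete data | 0.65 | 0.75 | 0.85 | 0.90 |
| Planned single-visit power (adjusted 80%) | 62% | 68% | 73% | 76% |
| Noncentrality ratio, sustained effect | 0.53 | 0.67 | 0.80 | 0.87 |
| Planned 2-df power, sustained (constrained 80%) | 52% | 62% | 70% | 74% |
| Noncentrality ratio, week 4 only | 0.82 | 0.89 | 0.94 | 0.96 |
| Planned 2-df power, week 4 only (constrained 80%) | 71% | 75% | 77% | 78% |
| Variance ratio, 20% missing | 0.70 | 0.79 | 0.87 | 0.92 |
| Detectable difference, planned (SD) | 0.302 | 0.257 | 0.200 | 0.164 |
| Detectable difference, constrained (SD) | 0.252 | 0.228 | 0.187 | 0.157 |
| Variance ratio, k = 1.25, complete data | 0.78 | 0.89 | 0.98 | 1.00 |
| Variance ratio, outcome 4 | 0.84–0.90 | 0.89–0.93 | 0.94–0.96 | 0.96–0.98 |

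**Outcome 4.** Selecting women on baseline drinking shrinks the baseline variance to v. For a bivariate normal measure truncated by that selection, the ratio is (1 + ρ)/[(1 + ρ) + v(1 − ρ)]. If the top 20% to 50% are selected (assumed), v is 0.22 to 0.36, which gives the last row. The follow-up SD is then 1.28 to 2.06 times the baseline SD, so little is left to gain.

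**Does the ordering ever reverse?** Over 5,000 random covariance matrices and three missingness patterns, the smallest ratio of free to constrained variance was 1.000.

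**The case against.** The strongest reply is that nothing here is an error. The protocol words most of these outcomes as change and section 14.2 announces change from baseline, and the SAP delivers exactly that with a valid, conventional model. Under randomisation both analyses estimate the same effect, so this is a preference about efficiency on secondary outcomes in a self-described pilot. That is true, and it limits the weight of the point. It is no reason to prefer the less precise form.

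The size is also uncertain, and this stands. ρ is assumed, no effect sizes are given for the secondary outcomes, and the 80% anchor is a yardstick rather than this trial's power. At ρ of 0.7 to 0.8 with missing data, the detectable difference moves only from 0.200 to 0.187 SD and from 0.164 to 0.157 SD. Some measures are bounded day counts in a sample that includes non-drinkers, follow-up is by telephone while baseline is on site, and the SAP selects the covariance by AIC. Equal SDs and compound symmetry are therefore idealisations. The ordering survives these departures; the percentages may not.

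Two technical limits also stand. The ordering holds like for like: at ρ = 0.95 with 20% dropout, the planned model slightly beats a completers-only week-12 analysis of covariance (variance ratio 0.994). And modelling only post-baseline visits with baseline as covariate leaves out women with no follow-up, which fits poorly with the protocol's commitment to analyse all randomised participants. The common-baseline-mean form does not have this drawback.

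**Conclusion.** The concern holds. The planned contrasts for the continuous measures in secondary outcomes 3, 4, 5, 8 and 9 are valid change-score contrasts. In large samples, with the same data and a correctly specified covariance, they are never more precise than baseline-adjusted ones; estimating the baseline slope costs only about 0.2% of variance at this sample size.

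With equal SDs and ρ between 0.3 and 0.8, the excess variance is worth 4 to 18 points of single-visit power against an 80% reference, and 6 to 28 points on the joint test for a sustained effect. At ρ = 0.7, matching the constrained joint test would take 1/0.80 = 1.25 times as many participants. The gain is small in outcome 4, and is nil at ρ = 0.8 if the follow-up SD is 1.25 times the baseline SD.

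The change is worth making because it costs almost nothing, but it ranks below any point on the primary analysis. The direction is certain; the size rests on correlations that the documents do not give.

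**What to change.** In the SAP, replace the treatment, time and interaction model for continuous outcomes with one that has time as a factor, arm-by-visit terms at post-baseline visits only, and no arm effect at week 0. Week 0 stays in the response, so all randomised women with a baseline value remain in the model. Modelling the post-baseline visits with baseline as covariate is a second-best alternative.

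Keep one joint 2-df test of the arm effect at weeks 4 and 12 as the overall test, so the number of overall tests does not grow. For outcome 5 use the single 1-df week-4 contrast. Report the week-4 and week-12 contrasts with 95% confidence intervals, and test them only after the joint test or with the adjustment that protocol 14.2 foresees ("Statistical analyses will be adjusted for multiple comparisons when indicated").

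No new data or software is needed. The one real cost is timing: the SAP is dated 18 February 2022, after the planned last follow-up in November 2021. If unblinded data had already been seen, the change must be dated, disclosed and reported alongside the planned test.
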